	
pathology reports that include notes such as: borderline, cannot exclude melanoma, cannot exclude early evolving melanoma, unusual features, atypical spitz nevi, suspicion for melanoma, re-excision (or further removal) should be considered or is recommended in the pathologist management comment), Squamous cell carcinoma, Basal cell carcinoma).
 
The Study protocol will also compare the accuracy of the Sklip System when used by a layperson (Participant) versus near-perfect Sklip System user (Study Coordinator), assess whether Sklip System improves triage of PSLCs < 6 mm in diameter and triage of thin melanomas with <0.8 mm Breslow depth as suspicious, as compared to the current medical provider virtual triage method that relies on store-and-forward of smartphone clinical images (SCI), and assess accuracy of layperson-performed self-skin-exams (SSEs) at-home in the identification of all suspicious PSLCs present on their body as compared to the same layperson (Participant) evaluated with a full body skin examination (FBSE) by a dermatology Provider (DP) in-person.

Primary Objective	
The Sklip System enables laypersons to safely triage self-selected pigmented skin lesions of concern (PSLCs) from home with the same or better accuracy than pre-specified performance goals* for detection of PSLCs that require biopsy and are malignant: Melanoma and atypical melanocytic nevi with uncertain malignant potential (moderate, severe, and high grade atypia; those with pathology reports that include notes such as: borderline, cannot exclude melanoma, cannot exclude early evolving melanoma, unusual features, atypical spitz nevi, suspicion for melanoma, re-excision (or further removal) should be considered or is recommended in the pathologist management comment) (<math>\geq 95\%</math> sensitivity, <math>\geq 30\%</math> specificity), Squamous cell carcinoma (<math>\geq 80\%</math> sensitivity, <math>\geq 30\%</math> specificity), Basal cell carcinoma (<math>\geq 80\%</math> sensitivity, <math>\geq 30\%</math> specificity).

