Exploratory Objectives	
 
1. To compare the accuracy of Sklip System triage when used by a layperson versus near-perfect Sklip System user
 
2. To assess whether Sklip System improves triage of pigmented skin lesions of concern < 6mm in diameter as suspicious as compared to the current medical provider virtual triage method that relies on store-and-forward non-medical-device assisted smartphone clinical images
 
3. To assess whether Sklip System improves triage of thin melanomas with < 0.8 mm Breslow depth as suspicious as compared to the current medical provider virtual triage method that relies on store-and-forward non-medical-device assisted smartphone clinical images
 
4. To determine the accuracy of layperson-performed self-skin-exam(s) at-home in the identification of all suspicious pigmented skin lesions of concern present on their body as compared to the same layperson evaluated with full body skin examination by a dermatology Provider in-office
 

*Pre-specified Performance Goals	
*Pre-specified performance goals have been reviewed with the FDA for testing the Sklip System (including SMSA) as a stand-alone device.

Participant activity prior to the At-home Phase	
A copy of the Participant Mole Log Sheet (PMLS) will be provided to Participants at the beginning of the At-home Phase. All Participants will be administered a pre-survey at the start of the Study to assess baseline knowledge and comfort in performing a SSE as well as a post-survey at the end of the Study.

Blinding	
The Study Site PIs and DPs will be fully blinded to all results of the At-home Phase, including the PMLS. Participants will be informed of the blinding activity prior to their FBSE to avoid DP selection-bias. Specifically, the dermatology provider will be instructed to say the following to each participant upon entering

	
the patient room for the in-person FBSE: “Hello, my name is [name and title], the purpose of today’s visit is to complete a full body skin examination as part of the at-home dermatoscopy study. To avoid bias, please hold with any questions related to your moles of concern until I have verified that I completed your full body skin examination and all other study related activities. I will be happy to address your questions or concerns at that time.”

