## 2. OBJECTIVES AND ENDPOINTS

### 2.1 PRIMARY OBJECTIVES AND ENDPOINTS

Primary Objective	Endpoint	Start	End
Sklip System enables laypersons to safely triage self-selected pigmented skin lesions of concern from home with the same or better accuracy than pre-specified performance goals* for	Using all Participant PSLCs recorded in the Participant Mole Log Sheets, triage accuracy measures of the SMSA output of Participant-taken DDI will be assessed using a 2x2 table,	First day of enrollment	Up to 42 days after first day of enrollment

detection of pigmented skin lesions that require biopsy:
 
Melanoma and atypical melanocytic nevi with uncertain malignant potential (moderate, severe, and high grade atypia; those with pathology reports that include notes such as: borderline, cannot exclude melanoma, cannot exclude early evolving melanoma, unusual features, atypical spitz nevi, suspicion for melanoma, re-excision (or further removal) should be considered or is recommended in the pathologist management comment): ≥95% sensitivity, ≥30% specificity
 
Squamous cell carcinoma: ≥80% sensitivity, ≥30% specificity
 
Basal cell carcinoma: ≥80% sensitivity, ≥30% specificity
 
*Pre-specified performance goals have been reviewed with the FDA for testing the Sklip System (including SMSA) as a stand-alone device.
	
where the SMSA rating of “SUSPICIOUS” or “UNREMARKABLE” will be estimated to pre-specified accuracy metrics discussed with the FDA.
 
The Sensitivity of the SMSA using Participant-taken DDI will be estimated to pre-specified performance goals described in sections above, using 0.05 significance level and 10% margin of error.
 
Triage accuracy measures of the Sklip System (specificity, negative predictive value, positive predictive value, and accuracy) will also be calculated.
 
The Ground Truth will be the combination of the following described in the Sections above:
 
Dataset N) DDI dermoscopic diagnosis ground truth (DDI-GT) for PSLCs that were not biopsied during the In-Person Phase, and
 
Dataset O) Histologic diagnosis ground truth (H-GT) for lesions that were biopsied during the In-Person Phase
		
---	--	--	--

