### 11. STATISTICAL CONSIDERATIONS

#### 11.1 STATISTICAL AIM

The statistical aim of this pivotal trial is the estimation of diagnostic accuracy of the Sklip System estimated to pre-specified criteria: 95% sensitivity and 30% specificity for **Melanoma and atypical melanocytic nevi with uncertain malignant potential** (moderate, severe, and high grade atypia; those with pathology reports that include notes such as: borderline, cannot exclude melanoma, cannot exclude early evolving melanoma, unusual features, atypical spitz nevi, suspicion for melanoma, re-excision (or further removal) should be considered or is recommended in the pathologist management comment), 80% sensitivity and 30% specificity for **Squamous cell carcinoma**, 80% sensitivity and 30% specificity for **Basal cell carcinoma**.

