#### 11.2 SAMPLE SIZE DETERMINATION

Sample size was calculated using formulas based on normal approximation to the binomial distribution. Previously recorded historical biopsy results for Melanoma, Squamous cell carcinoma, and Basal cell carcinoma across the proposed Study Sites averaged 2.3%, 12.5% and 29.2% of in-person dermatology Provider visits (i.e. cases), respectively. This represents disease prevalence rates in this pivotal Study target population of interest (i.e. patients who visited a Study Site within a 365 day period specifically for a mole spot check with concern for skin cancer, or a full body skin exam (FBSE) for the purpose of skin cancer prevention. This calculation presumes the exclusion of all other dermatology visits not related to a concern for skin cancer. Formulae (1) and (2) were used to estimate the sample size needed to evaluate the sensitivity (Se) and specificity (Sp), based on the diagnostic performance data available for melanoma from the SMSA Performance Study, and the target population case prevalence rates. The following values are inserted:  $Z_{\alpha/2} = 1.96$  for  $\alpha = 0.05$  level of significance, and  $d = 10\%$  margin of error for 95% Confidence Interval.

$$n_{Se} = \frac{Z_{\frac{\alpha}{2}}^2 \widehat{Se} (1 - \widehat{Se})}{d^2 \times \text{Prev}} \quad (1)$$

$$n_{Sp} = \frac{Z_{\frac{\alpha}{2}}^2 \widehat{Sp} (1 - \widehat{Sp})}{d^2 \times (1 - \text{Prev})} \quad (2)$$

Table 4 and Table 5 below summarizes the sample size estimates for cutaneous diseases of interest to evaluate the sensitivity and specificity of the investigational device (Sklip System). As can be seen from the table, the size estimate calculated using the sensitivity value for detecting melanoma (423 cases [lesions]) yields the largest number. The expected numbers of lesions that will be accordingly captured during the Study are summarized in Table 6.

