Considering the larger number of cases required for evaluation of sensitivity (423 for Melanoma; based on SMSA performance of sensitivity for melanoma of 97.4%) as opposed to specificity (114 for SCC), a 49% specificity can be estimated from the hypothetical sample data. Previous peer-reviewed studies, exclusive to virtual visits, showed that participants submitted an average of 1.02 to 1.9 images per participant. Considering the aforementioned and average case submission rates reported by the proposed Study Sites, we expect a case submission rate of 1.5 per Study Participant. Assuming a 10% drop-out rate a total number of 310 Participants (dropout-inflated sample size) will be needed for the current study (310 = 423 ÷ 1.5 × 1.10).

**Table 4. Sample size estimates for cutaneous diseases of interest to evaluate the sensitivity of Sklip System based on the available target population prevalence data.**

Lesions	Sample Size Estimate to Test for Sensitivity											
	Melanoma			BCC			SCC			AMN		
	Confirmed	Excluded	Total	Confirmed	Excluded	Total	Confirmed	Excluded	Total	Confirmed	Excluded	Total
Suspicious	9	248	257	17	89	107	17	31	48	17	243	260
Non-Suspicious	1	165	166	1	38	39	1	13	14	1	104	105
Total Scanned	10	413	423	18	128	146	18	44	63	18	347	365
Prevalence	2.3%			12.5%			29.2%			5.0%		
Sensitivity	97.4%			95%			95%			95%		
Specificity	40%			30%			30%			30%		

The sample size was estimated using formulae (1) and (2) to test for sensitivity and specificity, respectively, with  $\alpha = 0.05$  significance level and 10% margin of error for 95% Confidence Interval. The respective sensitivity and specificity values were used to estimate the numbers of suspicious and non-suspicious lesions confirmed or excluded by the Ground Truth as described in the Sections above. BCC: Basal cell carcinoma, SCC: Squamous cell carcinoma, AMN: Atypical melanocytic nevi with uncertain malignant potential.

**Table 5.** Sample size estimates for cutaneous diseases of interest to evaluate the specificity of Sklip System based on the available target population prevalence data.

Sample Size Estimate to Test for Specificity											
Melanoma			BCC			SCC			AMN		
Confirmed	Excluded	Total	Confirmed	Excluded	Total	Confirmed	Excluded	Total	Confirmed	Excluded	Total
2	55	57	11	56	67	32	56	88	4	56	61
0	37	37	1	24	25	2	24	26	0	24	24
2	92	94	12	81	92	33	81	114	4	81	85
2.3%			12.5%			29.2%			5.0%		

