#### 11.4.2 ANALYSIS OF PRIMARY ENDPOINT(S)

For the Primary Endpoints, the SMSA outputs of “SUSPICIOUS” or “UNREMARKABLE” from Participant-taken DDI will be compared to the Ground Truth, described in the Sections above. For **Melanoma and atypical melanocytic nevi with uncertain malignant potential** (moderate, severe, and high grade atypia; those with pathology reports that include notes such as: borderline, cannot exclude melanoma, cannot exclude early evolving melanoma, unusual features, atypical spitz nevi, suspicion for melanoma, re-excision (or further removal) should be considered or is recommended in the pathologist management comment), a 2x2 table consisting of the following counts (number of PSLCs):

- True Positives (TP): the SMSA output of SUSPICIOUS agrees with the Ground Truth for PSLCs that were

biopsied and were diagnosed as Melanoma or atypical melanocytic nevi with uncertain malignant potential, using Dataset (O) (Histologic diagnosis ground truth (H-GT)),

- False Positives (FP): the SMSA output of SUSPICIOUS does not agree with the benign Ground Truth using Dataset (N) (DDI dermoscopic diagnosis ground truth) and Dataset (O)
- False Negatives (FN): the SMSA output of UNREMARKABLE does not agree with the Ground Truth for PSLCs that were biopsied and diagnosed as Melanoma or atypical melanocytic nevi with uncertain malignant potential using Dataset (O)
- True Negatives (TN): the SMSA output of UNREMARKABLE agrees with the benign Ground Truth, using both Dataset (N) and Dataset (O)

For **Melanoma and atypical melanocytic nevi with uncertain malignant potential**, Sensitivity ( $TP \div (TP + FN)$ ) of the Sklip System will be calculated with a lower one-sided 95% confidence interval using the Exact (Clopper-Pearson) method. For **Squamous cell carcinoma** and for **Basal cell carcinoma**, Sensitivity and lower one-sided confidence intervals will be estimated in the same manner as for Melanoma and atypical melanocytic nevi with uncertain malignant potential.

Specificity ( $TN \div (FP + TN)$ ) will be the same for Melanoma and atypical melanocytic nevi with uncertain malignant potential, SCC, and BCC, where:

- False Positives (FP): the SMSA output of SUSPICIOUS does not agree with the benign Ground Truth, using Dataset (N) and Dataset (O)
- True Negatives (TN): the SMSA output of UNREMARKABLE agrees with the benign Ground Truth, using Dataset (N) and Dataset (O)

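### The 10% margin that sets the sample size is not delivered by the planned exact intervals, and no primary goal says whether the estimate or the lower bound must meet it (for the 95% goal the bound cannot)

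*Combined protocol and SAP*

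**What the plan says.** Section 11.2 sizes the trial on precision: "Sample size was calculated using formulas based on normal approximation to the binomial distribution". The inputs for melanoma are a sensitivity of 97.4%, a prevalence of 2.3%, Z = 1.96 and d = 10%. Of the entities considered, "the size estimate calculated using the sensitivity value for detecting melanoma (423 cases [lesions]) yields the largest number". The note to Table 4 repeats the "significance level and 10% margin of error for 95% Confidence Interval". Table 6 then expects 10 melanomas, 21 atypical melanocytic nevi, 52 and 121 lesions for the two carcinomas, and 220 lesions negative for malignancy.

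The primary goals are at least 95% sensitivity for the composite of melanoma and atypical nevi, at least 80% sensitivity for each carcinoma, and at least 30% specificity. Section 2.1 says that sensitivity "will be estimated to pre-specified performance goals described in sections above, using 0.05 significance level and 10% margin of error". Section 11.1 says: "The statistical aim of this pivotal trial is the estimation of diagnostic accuracy of the Sklip System estimated to pre-specified criteria". The Synopsis objective is comparative: triage "from home with the same or better accuracy than pre-specified performance goals* for detection of PSLCs that require biopsy and are malignant".

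Under section 11.4.2, sensitivity "of the Sklip System will be calculated with a lower one-sided 95% confidence interval using the Exact (Clopper-Pearson) method". Specificity is treated the same way, and two-sided exact 95% intervals are added. The Synopsis notes that "Pre-specified performance goals have been reviewed with the FDA for testing the Sklip System (including SMSA) as a stand-alone device", but records no comparison rule.

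**The concern.** The planning method and the analysis method differ where the difference is largest: about 10 lesions and a sensitivity near 100%. A reader of 11.2 is told to expect 10% precision for the entity that set the sample size, and the plan's own intervals will be much wider.

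The plan also sets numerical goals and calculates a one-sided lower bound, yet gives no null hypothesis and no success criterion. If the bound is what must reach 95%, the planned number of composite lesions is too small even with a perfect result. If the estimate is what must reach 95%, one miss in 31 is allowed. Should this stay open until the data are seen, the conclusion on the lead goal of a trial that the plan calls pivotal could depend on a choice made afterwards.

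**Working it through.** **1. The plan's own figure.** Formula (1) with the 11.2 inputs:

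- 1.96² × 0.974 × 0.026 / (0.10² × 0.023) = 422.98, so 423 lesions.
- Melanomas: 423 × 0.023 = 9.7, about 10.
- Participants: 423 ÷ 1.5 × 1.10 = 310.2, so 310.
- Normal-approximation half-width at n = 10: 1.96 × √(0.974 × 0.026 / 10) = 9.9 points.

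The formula therefore delivers 10% by its own method. The expected number of misses is 10 × 0.026 = 0.26, far too few for that approximation.

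**2. Exact intervals for melanoma, n = 10.** The Clopper-Pearson lower limit is the α quantile of Beta(x, n−x+1). The upper limit is the 1−α quantile of Beta(x+1, n−x), or 100% when x = n. Two-sided 95% uses α = 0.025 per tail.

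| Result | Two-sided 95% | Half-width |
|---|---|---|
| 10/10 | 69.2% to 100% | 15.4 points |
| 9/10 | 55.5% to 99.7% | 22.1 points |

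Weighted by Binomial(10, 0.974), the expected half-width is 17.1 points.

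**3. The primary composite.** Table 6 gives 10 + 21 = 31 lesions (check: 423 × (0.023 + 0.050) = 30.9).

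| Result | Estimate | One-sided 95% lower bound | Two-sided 95% lower limit |
|---|---|---|---|
| 31/31 | 100% | 90.8% | 88.8% |
| 30/31 | 96.8% | 85.6% | 83.3% |
| 29/31 | 93.5% | 81.1% | 78.6% |

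With no misses the one-sided bound is 0.05^(1/n). It is 94.97% at n = 58 and 95.05% at n = 59. With one miss, 91/92 gives 94.95% and 92/93 just reaches 95.00%. So 59/59 or 92/93 is the bare minimum. At a true sensitivity of 97.4%, 59/59 would occur only 0.974^59 = 21% of the time. With no dropout at all, 310 × 1.5 = 465 lesions give 465 × 0.073 = about 34 composite lesions and a ceiling of 0.05^(1/34) = 91.6%.

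**4. The 10% margin for the composite.** Weighted by Binomial(31, Se), the expected two-sided half-width is 7.6 points at true 97.4% and 9.1 at true 95%. The interval is lopsided: the lower limit lies on average 12.8 and 14.0 points below the estimate.

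**5. How much the unstated rule matters.**

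- *95% goal, n = 31.* 31/31 and 30/31 meet the goal on the estimate and not on the bound. Their combined probability is 81% at true 97.4%, 54% at true 95% and 17% at true 90%.
- *80% goals.* At n = 52, 42 to 46 correct meet 80% on the estimate only (46/52: bound 78.5%; 47/52: 80.8%). At n = 121, the range is 97 to 104 (104/121: 79.7%; 105/121: 80.6%). At true 85% these zones have probability 66% and 60%. At true 95%, the Table 4 value, the bound clears 80% with probability 95.5% and above 99.9%.
- *30% specificity goal, n = 220.* 66 to 77 correct meet 30% on the estimate only (77/220: bound 29.7%; 78/220: 30.1%).

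The choice matters for every goal. Only the 95% goal is out of the bound's reach at the expected count.

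**The case against.** The strongest reply is that this is an estimation study. Section 11.1 says so, 11.4.2 defines sensitivity as TP ÷ (TP + FN), and the goal is a sensitivity of at least 95%. On that wording the estimate is compared with the goal, the bound is supporting information, and the 90.8% ceiling harms nothing. This reading is tenable. It is not settled, because 2.1 attaches a 0.05 significance level, 11.4.2 puts the one-sided bound first, and the notes to Tables 4 and 5 speak of testing. A rule may have been agreed with the FDA, but it is not in the plan.

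Three further replies stand in part.

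- *The 423 is not an arithmetic error.* This is correct: the named method gives 9.9 points. The mismatch is with the analysis method.
- *Melanoma alone is not a primary endpoint.* This is also correct. Section 11.4.2 plans no melanoma-only interval, and the melanoma calculation served to find the largest sample size. What remains is a precision statement that the plan's exact method would not bear out.
- *The 10% margin in 2.1 holds for the composite.* It does so on average as a half-width, but not as the distance down to the lower limit, which is the direction that matters for a minimum-sensitivity goal.

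A reader might infer that the trial is bound to fail its lead goal. The documents do not support that, because they nowhere make the bound the criterion.

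**Conclusion.** The point holds in a limited form. The 10% margin in 11.2 is not delivered by the plan's exact method at about 10 melanomas: the half-width is 15.4 points with no misses and 22.1 with one. At 31 composite lesions the one-sided bound cannot exceed 90.8%, so the planned size does not support a bound-based claim of at least 95%. The plan does not say which quantity is compared with the 95%, 80% or 30% goals. On the lead goal that choice would decide the outcome in 81% of trials at true 97.4% and 54% at true 95%.

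This rests on the Table 6 totals holding for lesions that participants select themselves, on no loss to three ERROR outputs or missing data (losses would lower the ceiling), and on lesions being independent, as the exact method assumes. Only the totals of Table 6 are used. Its suspicious counts for the carcinomas (36 of 52 and 84 of 121, about 69%) do not match the 95% in Table 4, so the chances given at true 95% depend on Table 4. The text of 11.2 assigns 12.5% and 29.2% to the opposite carcinomas from the tables. Both have the same 80% goal, so nothing here changes.

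**What to change.** 1. **Section 11.2.** Replace the 10% margin with exact precision at the expected counts, for example:

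> At about 10 melanomas the exact two-sided 95% interval is 69.2% to 100% with no misses (half-width 15.4 points) and 55.5% to 99.7% with one miss (22.1 points). At about 31 melanoma or atypical-nevus lesions the exact one-sided 95% lower bound is 90.8%, 85.6% and 81.1% with 0, 1 and 2 misses. The two-sided lower limit is 88.8% for 31/31 and 83.3% for 30/31.

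2. **Section 2.1.** State that the 10% margin for the composite holds on average only as a half-width (expected 7.6 points at true 97.4%, 9.1 at true 95%), and that the lower limit lies about 13 to 14 points below the estimate.

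3. **Sections 2.1 and 11.4.2.** Before data are seen, state for each goal, sensitivity and specificity, whether the estimate or the exact one-sided lower bound is compared with it, consistent with what was reviewed with the FDA. Acknowledge that the planned size does not support a bound-based claim of at least 95% for the composite.

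The cost is wording only, with no added participants or data. The downside is that the stated precision becomes less favourable. If the rule reviewed with the FDA turns out to be the bound, the sponsor faces a decision on sample size or goal that wording does not settle.

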Key Exclusion Criteria	
Participants who self-identify having Fitzpatrick Skin Types 5 and 6, visionally impaired adults, pregnant and breastfeeding mothers. Participants who have had a skin check visit with a dermatology Provider within the last 90 days will be excluded to avoid self-selection bias, unless the Participant identifies a new unexamined (not previously documented) spot of concern. Vulnerable populations including children, prisoners, and decisionally impaired adults, will not be eligible for this Study. The Sklip System output is currently only available in English language, therefore non-English speaking Participants are not eligible.

Skin lesions not applicable for SMSA evaluation	
Sklip System instructions and product labelling clearly define specific device limitations and suggest the Participant (user) to contact their healthcare Provider with their PSLC as part of normal clinical care, when the target PSLC does not qualify, or if the user does not understand the SMSA output result. The following anatomical locations, Fitzpatrick Skin Types and skin lesion types are not applicable for SMSA evaluation:
 
Non-qualified anatomical areas: images of skin lesions taken from a non-sun exposed area (eyes, mucosal membranes (eyelids, medial canthi, mouth, anus, genitals)), hidden or not flat areas (nails, ears, perinasal fold, conchal bowl, intergluteal cleft, perianal skin and interdigital spaces) and/or acral lesions (palms of hands and soles of feet).
 
Not applicable Fitzpatrick Skin Types: 5 and 6

	Pink skin lesions: a skin lesion (mole) that does not contain any pigment, contains only white, pink, red or uniform-homogenous color similar to the surrounding skin within its surface area, contains less than five (5) percent pigment within the skin lesion surface area or clearly defined in-focus vasculature that can be visualized with a dermatoscope (i.e. actinic keratosis without pigment, clinically and dermoscopically pink melanocytic nevi, amelanotic melanoma, basal cell carcinoma or squamous cell carcinoma without any pigment).

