Definition of Pigment qualified for Sklip System	Pigment is defined as any color other than the surrounding skin phototype that delineates a skin lesion from the background that can be visualized with a dermatoscope. This includes: light brown, dark brown, black, white, blue, grey, purple, red, pink, yellow, and orange (including clearly distinguishable vascular patterns within the skin lesion surface area).
Follow-up Duration	After conclusion of the Study intervention, the EMR(s) of all enrolled Participants will be monitored for any relevant data obtained from follow up (as part of standard clinical pathways). An attempt to contact Participants lost to follow-up will be made for up to 30 days.
Duration of Therapy	There is no therapy as part of this Study.
Sponsor Monitoring	The Sponsor will conduct periodic monitoring of the Study Site data handling practices on REDCap Cloud every 45 days on at least one (1) instance to verify the integrity of the source data. This will be done in person or virtually with an approved Study Site representative responsible for REDCap Cloud use and data handling. At the end of the Study, ten percent (10%) of the source data will be re-evaluated by the Sponsor to re-verify the integrity of the source data.
Interim Data Analysis	There will not be any interim data analysis during this Study.
Medical costs during the In-Person Phase	All medical services that fall under the normal clinical care pathway including: scheduling, triage, spot check, FBSE, biopsy, diagnosis and treatment (when applicable), will not be covered by the Study Sponsor and will be billed by Study Sites directly to patient insurance, or required to be paid out pocket.
Final Disposition of the Sklip dermatoscope and Sklip System access	All Participants will be able to keep their Sklip dermatoscope at the end of the Study, at no cost. SMSA access will expire within fourteen (14) days of confirmed delivery of the Sklip dermatoscope at the home address of the Participant.

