97.4%			95%			95%			95%		
40%			30%			30%			30%		

The sample size was estimated using formulae (1) and (2) to test for sensitivity and specificity, respectively, with  $\alpha = 0.05$  significance level and 10% margin of error for 95% Confidence Interval. The respective sensitivity and specificity values were used to estimate the numbers of suspicious and non-suspicious lesions confirmed or excluded by the Ground Truth as described in the Sections above. BCC: Basal cell carcinoma, SCC: Squamous cell carcinoma, AMN: Atypical melanocytic nevi with uncertain malignant potential.

**Table 6.** Numbers of PSLCs expected to be captured in the estimated sample from the target population.

Lesions	Melanoma Confirmed	Melanoma Excluded	BCC	SCC	AMN	Total non- Melanoma Cancers	Total Malignant Lesions	Total Negative for Malignancy Lesions	Total
Suspicious	9	248	36	84	14	135	144	113	257
Non-Suspicious	0	165	15	36	6	58	58	107	166
Total	10	413	52	121	21	193	203	220	423
Prevalence	2.3%	97.7%	12.5%	29.2%	5.0%	46.7%	49.0%	51.0%	100%
Lesions per Melanoma	1	42	5	13	2	20	21	22	43

A review of all histologically confirmed Melanoma diagnosis made at OHSU within the past 10 years revealed over 3,500 cases. A review of all histologically confirmed non-Melanoma skin cancer diagnosis made at OHSU within the past 5 years revealed over 30,000 cases. Based off these findings, since three (3) additional Satellite Study Sites are each required to contribute at least fifteen (15) percent of the total sample size each, a maximum of 124 Participants at Site #1 OHSU (FDA suggested maximum enrollment cap of 40%) and a minimum of 47 participants (FDA suggested minimum enrollment of 15%) at each additional Site is feasible.

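### Table 6's SCC and BCC yields (52 and 121) come from biopsy rates with no stated pigment or body-site restriction, so they are upper limits of unknown slack for two primary goals

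*Combined protocol and SAP*

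**What the plan says.** Section 11.2 takes its planning rates from site history: "Previously recorded historical biopsy results for Melanoma, Squamous cell carcinoma, and Basal cell carcinoma across the proposed Study Sites averaged 2.3%, 12.5% and 29.2" per cent "of in-person dermatology Provider visits (i.e. cases), respectively". The source population is "patients who visited a Study Site within a 365 day period specifically for a mole spot check with concern for skin cancer", or for a full body skin exam, with unrelated dermatology visits left out. Pigment and body site are not mentioned. Table 6, titled "Numbers of PSLCs expected to be captured in the estimated sample from the target population", shows 52 lesions at 12.5% and 121 at 29.2% out of 423. By the order of the text, 12.5% is SCC and 29.2% is BCC. Tables 4 to 6 label them the other way round.

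The Synopsis list of lesions not applicable for SMSA evaluation includes "basal cell carcinoma or squamous cell carcinoma without any pigment", any lesion that "contains less than five (5) percent pigment within the skin lesion surface area", and sites such as eyelids, ears and the perinasal fold. Section 6.1.1 adds nodular lesions. The next Synopsis entry, which defines qualifying pigment, is much wider: "This includes: light brown, dark brown, black, white, blue, grey, purple, red, pink, yellow, and orange", together with distinguishable vascular patterns.

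Sections 2.1 and 11.1 set a sensitivity goal of 80% for each of SCC and BCC. Section 11.4.2 reports each with a one-sided 95% Clopper-Pearson lower limit. Section 11.2 plans for a 0.05 "significance level and 10% margin of error for 95% Confidence Interval". No section says which result counts as meeting a goal.

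**The concern.** The rates describe biopsied SCC and BCC at visits for a skin cancer concern. The trial collects pigmented lesions that a layperson can scan. If some historical carcinomas were unpigmented or at sites the device does not cover, the same rates cannot be carried unchanged into a count of pigmented lesions. That mismatch would remain even if rates per visit were properly converted to rates per lesion.

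SCC and BCC account for two of the three primary sensitivity goals. The sample size is driven by melanoma (423 lesions), and SCC and BCC look safe only because Table 6 shows a surplus over the 18 confirmed lesions per entity in Table 4. Section 11.2 sets no minimum count per entity, and no interim look is planned that could reveal a shortfall.

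**Working it through.** **1. The plan's own figures.** Formula (1) is n = 1.96² × Se × (1 − Se) / (d² × Prev), with d = 0.10.
- Melanoma: 3.8416 × 0.974 × 0.026 / (0.01 × 0.023) = 422.98, stated as 423.
- The 12.5% column, Se 95%: 145.98, stated as 146.
- The 29.2% column, Se 95%: 62.49, stated as 63.
- Participants: 423 / 1.5 × 1.10 = 310.2, stated as 310.
- Table 6: 423 − 10 melanomas = 413; 413 × 0.125 = 51.6 (52) and 413 × 0.292 = 120.6 (121).

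All reproduce. No factor for pigment or site enters, so Table 6 implies a qualifying share of 100%.

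**2. Qualifying share.** Let f be the share of the historical carcinomas that would qualify. The documents do not give f, so it is an assumption, shown over a range. Expected counts are 52f and 121f.

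**3. Count needed under an assumed pass rule.** Assume the one-sided 95% exact lower bound must exceed 80%. With every lesion detected, the bound is 0.05^(1/n): 79.4% for n = 13 and 80.7% for n = 14. So 14 lesions with no miss is the minimum; one miss needs 22 lesions and two misses need 30. No result can pass if f is below 14/52 = 27% or 14/121 = 12%, respectively.

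**4. Chance of passing, true sensitivity 95%** (the value planned in Table 4), exact binomial:

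| Share f | 52-lesion entity: count, misses allowed, chance | 121-lesion entity: count, misses allowed, chance |
|---|---|---|
| 100% | 52, 5, 96% | 121, 16, >99% |
| 75% | 39, 3, 87% | 91, 11, >99% |
| 50% | 26, 1, 62% | 60, 6, 97% |
| 25% | 13, cannot pass, 0% | 30, 2, 81% |
| 10% | 5, cannot pass, 0% | 12, cannot pass, 0% |

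The Synopsis reports sensitivities of 97.0% (SCC) and 97.3% (BCC). At 97%, 26 lesions give 82% and 30 lesions give 94%.

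**5. The plan's own precision target.** Formula (1) at Se 95% needs 3.8416 × 0.95 × 0.05 / 0.01 = 18.25 confirmed lesions. Out of 423 this requires:
- 12.5% entity: f of at least 18.25 / (423 × 0.125) = 18.25 / 52.9 = 35%;
- 29.2% entity: f of at least 18.25 / (423 × 0.292) = 18.25 / 123.5 = 15%.

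Below those shares the 10% margin is not delivered. At f = 25% the 12.5% entity would need 18.25 / 0.03125 = 584 lesions. With 13 confirmed lesions the margin is 1.96 × √(0.95 × 0.05 / 13) = 11.8%.

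**The case against.** Several points on the other side have force.

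- **The wide definition of pigment.** If white, red and pink count, many clinically pink carcinomas could qualify and the overstatement could be small. This stands. It conflicts with the not-applicable list, and the documents do not say which governs.
- **Unrestricted rates are an inference.** A reader might take the text to say that every biopsied SCC and BCC was counted. It is silent on pigment and does restrict the type of visit. One sentence in Section 11.2 could settle the matter.
- **Body sites.** A reader might infer that lesions on ears or eyelids leave the analysis. Section 3.1 has coordinators take control images of lesions at non-qualified sites, Section 2.1 uses all lesions in the log sheets, and Section 11 states no site exclusion. Whether such lesions count is open.
- **Testability.** A reader might infer that the 80% goals cannot be tested. That needs both a pass rule on the lower bound, which is not written, and a share below 27% or 12%, which nothing in the documents supports. Section 11.1 states the aim as estimation. If the point estimate is what counts, there is no minimum number: with 13 lesions and true sensitivity 95%, the chance of observing at least 80% is 97.5%. The cost is then precision.
- **Which entity.** A reader might attach the smaller counts to SCC. The text supports that; Tables 4 to 6 support BCC.

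None of this justifies the implied share of 100%. It limits what can be said about size.

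**Conclusion.** The multiplication in Table 6 is correct; the unsupported part is the assumption behind it. With the other planning assumptions held, 52 and 121 are upper limits for lesions qualifying under the not-applicable list. The documents do not allow a corrected figure.

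The entity at 12.5% is the fragile one: its chance of passing falls to 62% if half its lesions qualify, and below a share of about 35% it also misses the plan's own 10% margin. The entity at 29.2% is robust unless the share is around a quarter or less. Which disease is in which position cannot be told until the labels are corrected. The chances rest on three assumptions: the share, a true sensitivity of 95%, and a pass rule on the one-sided lower bound.

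**What to change.** 1. Reconcile the two Synopsis entries on pigment, and say whether lesions at non-qualified body sites count in the primary analysis.
2. Reconcile the SCC and BCC labels between the text of Section 11.2 and Tables 4 to 6.
3. Restate Table 6 from the sites' rates for qualifying lesions. If the records do not code pigment, show expected counts over a range of shares and mark 52 and 121 as upper limits.
4. Give the exact lower bound and the margin attainable for each entity at the fixed 310 participants, and restate the 10% margin where it is not met. Simply putting lower rates through formula (1) would not leave the sample size alone, because below a share of about 35% the 12.5% entity would need more than 423 lesions.
5. Write the pass rule in advance. If it is on the lower bound, report any entity with fewer than 14 confirmed lesions as descriptive. Fourteen is a floor for the test to be possible, not an adequate number: at 14 lesions and sensitivity 95% the chance of passing is 49%.

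The cost is a query of existing pathology records where they code pigment, and a revised Section 11.2. The downside is that the stated yields and precision become less favourable.
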